6.1.2.9 Dermatologic Events

Treatment-emergent rash has been associated with atezolizumab. The majority of cases of rash were mild in severity and self-limiting, with or without pruritus. Although uncommon, cases of severe cutaneous adverse reactions such as Stevens–Johnson syndrome and toxic epidermal necrolysis have been reported with atezolizumab. A dermatologist should evaluate persistent and/or severe rash or pruritus. A biopsy should be considered unless contraindicated.

Management guidelines for dermatologic events are provided in the table below.

Event	Management
Dermatologic event, Grade 1	
• Continue atezolizumab.• Consider treatment with topical corticosteroids and/or other symptomatic therapy (e.g., antihistamines).
Dermatologic event, Grade 2	
• Continue atezolizumab.• Consider patient referral to dermatologist for evaluation and, if indicated, biopsy.• Initiate treatment with topical corticosteroids.• Consider treatment with higher-potency topical corticosteroids if event does not improve.• If unresponsive to topical corticosteroids, consider oral prednisone

	0.5 mg/kg/day.
Dermatologic event, Grade 3	
Withhold atezolizumab for up to 12 weeks after event onset.^aRefer patient to dermatologist for evaluation and, if indicated, biopsy.Initiate treatment with corticosteroids equivalent to 10 mg/day oral prednisone, increasing dose to 1–2 mg/kg/day if event does not improve within 48–72 hours.If event resolves to Grade 1 or better, resume atezolizumab.^bIf event does not resolve to Grade 1 or better while withholding atezolizumab, permanently discontinue atezolizumab.^c
Dermatologic event, Grade 4	
Permanently discontinue atezolizumab.^c
Stevens-Johnson syndrome or toxic epidermal necrolysis (any grade)	
Additional guidance for Stevens-Johnson syndrome or toxic epidermal necrolysis:
 
Withhold atezolizumab for suspected Stevens-Johnson syndrome or toxic epidermal necrolysis.Confirm diagnosis by referring patient to a specialist (dermatologist, ophthalmologist, or urologist as relevant) for evaluation and, if indicated, biopsy.Follow the applicable treatment and management guidelines above.If Stevens-Johnson syndrome or toxic epidermal necrolysis is confirmed, permanently discontinue atezolizumab.

^a Atezolizumab may be withheld for a longer period of time (*i.e.*, >12 weeks after event onset) to allow for corticosteroids (if initiated) to be reduced to the equivalent of ≤10 mg/day oral prednisone. The acceptable length of the extended period of time must be based on an assessment of benefit–risk by the investigator and in alignment with the protocol requirements for the duration of treatment and documented by the investigator.

^b If corticosteroids have been initiated, they must be tapered over ≥1 month to the equivalent of ≤10 mg/day oral prednisone before atezolizumab can be resumed.

^c Resumption of atezolizumab may be considered in patients who are deriving benefit and have fully recovered from the immune-mediated event. The decision to re–challenge patients with atezolizumab should be based on investigator's assessment of benefit–risk and documented by the investigator (or an appropriate delegate).

6.1.2.10 Immune-mediated Meningoencephalitis

Immune-related meningoencephalitis is an identified risk associated with the administration of atezolizumab. Immune-related meningoencephalitis should be suspected in any patient presenting with signs or symptoms suggestive of meningitis or encephalitis, including, but not limited to, headache, neck pain, confusion, seizure, motor or sensory dysfunction, and altered or depressed level of consciousness. Encephalopathy from metabolic or electrolyte imbalances needs to be distinguished from potential meningoencephalitis resulting from infection (bacterial, viral, or fungal) or progression of malignancy, or secondary to a paraneoplastic process.

All patients being considered for meningoencephalitis should be urgently evaluated with a CT scan and/or MRI scan of the brain to evaluate for metastasis, inflammation, or edema. If deemed safe by the treating physician, a lumbar puncture should be performed, and a neurologist should be consulted.

Patients with signs and symptoms of meningoencephalitis, in the absence of an identified alternate etiology, should be treated according to the guidelines in the table below.

Event	Management
Immune-mediated meningoencephalitis, all grades	
• Permanently discontinue atezolizumab.^a• Refer patient to neurologist.• Initiate treatment with corticosteroids equivalent to 1–2 mg/kg/day IV methylprednisolone and convert to 1–2 mg/kg/day oral prednisone or equivalent upon improvement.• If event does not improve within 48 hours after initiating corticosteroids, consider adding an immunosuppressive agent.• If event resolves to Grade 1 or better, taper corticosteroids over ≥1 month.

^a Resumption of atezolizumab may be considered in patients who are deriving benefit and have fully recovered from the immune-mediated event. The decision to re-challenge patients with atezolizumab should be based on investigator's assessment of benefit–risk and documented by the investigator (or an appropriate delegate).

6.1.2.11 *Neurologic disorders*

Myasthenia gravis and Guillain-Barré syndrome have been observed with single-agent atezolizumab. Patients may present with signs and symptoms of sensory and/or motor neuropathy. Diagnostic work-up is essential for an accurate characterization to differentiate between alternative etiologies. Management guidelines for neurologic disorders are provided in table below.

Event	Management
Immune-mediated neuropathy, Grade 1	
• Continue atezolizumab.• Investigate etiology.
Immune-mediated neuropathy, Grade 2	
• Withhold atezolizumab for up to 12 weeks after event onset.^a• Investigate etiology and refer patient to neurologist.• Initiate treatment as per institutional guidelines.• If event resolves to Grade 1 or better, resume atezolizumab.^b• If event does not resolve to Grade 1 or better while withholding atezolizumab, permanently discontinue atezolizumab.^c
Immune-mediated neuropathy, Grade 3 or 4	
• Permanently discontinue atezolizumab.^c• Refer patient to neurologist.• Initiate treatment as per institutional guidelines.

Myasthenia gravis and Guillain-Barré syndrome (any grade)	
• Permanently discontinue atezolizumab.^c• Refer patient to neurologist.• Initiate treatment as per institutional guidelines.• Consider initiation of corticosteroids equivalent to 1–2 mg/kg/day oral or IV prednisone.
---	---

^a Atezolizumab may be withheld for a longer period of time (*i.e.*, >12 weeks after event onset) to allow for corticosteroids (if initiated) to be reduced to the equivalent of ≤10 mg/day oral prednisone. The acceptable length of the extended period of time must be based on an assessment of benefit–risk by the investigator and in alignment with the protocol requirements for the duration of treatment and documented by the investigator.

^b If corticosteroids have been initiated, they must be tapered over ≥1 month to the equivalent of ≤10 mg/day oral prednisone before atezolizumab can be resumed.

^c Resumption of atezolizumab may be considered in patients who are deriving benefit and have fully recovered from the immune-mediated event. The decision to re–challenge patients with atezolizumab should be based on investigator's assessment of benefit–risk and documented by the investigator (or an appropriate delegate).

6.1.2.12 Renal Events

Immune-mediated nephritis has been associated with the administration of atezolizumab. Eligible patients must have adequate renal function. Renal function, including serum creatinine, should be monitored throughout study treatment. Patients with abnormal renal function should be evaluated and treated for other more common etiologies (including prerenal and postrenal causes, and concomitant medications such as non-steroidal anti-inflammatory drugs). Refer the patient to a renal specialist if clinically indicated. A renal biopsy may be required to enable a definitive diagnosis and appropriate treatment.

Patients with signs and symptoms of nephritis, in the absence of an identified alternate etiology, should be treated according to the guidelines in the table below.

Event	Management
Renal event, Grade 1	
• Continue atezolizumab.• Monitor kidney function, including creatinine and urine protein, closely until values resolve to within normal limits or to baseline values.
Renal event, Grade 2	
• Withhold atezolizumab for up to 12 weeks after event onset.^a• Refer patient to renal specialist.• Initiate treatment with corticosteroids equivalent to 1–2 mg/kg/day oral prednisone.• If event resolves to Grade 1 or better, resume atezolizumab.^b• If event does not resolve to Grade 1 or better while withholding atezolizumab, permanently discontinue atezolizumab.^c

Renal event, Grade 3 or 4	
• Permanently discontinue atezolizumab.• Refer patient to renal specialist and consider renal biopsy.• Initiate treatment with corticosteroids equivalent to 1–2 mg/kg/day oral prednisone.• If event does not improve within 48 hours after initiating corticosteroids, consider adding an immunosuppressive agent.• If event resolves to Grade 1 or better, taper corticosteroids over ≥ 1 month.
---------------------------	---

^a Atezolizumab may be withheld for a longer period of time (*i.e.*, >12 weeks after event onset) to allow for corticosteroids (if initiated) to be reduced to the equivalent of ≤ 10 mg/day oral prednisone. The acceptable length of the extended period of time must be based on an assessment of benefit–risk by the investigator and in alignment with the protocol requirements for the duration of treatment and documented by the investigator.

^b If corticosteroids have been initiated, they must be tapered over ≥ 1 month to the equivalent of ≤ 10 mg/day oral prednisone before atezolizumab can be resumed.

^c Resumption of atezolizumab may be considered in patients who are deriving benefit and have fully recovered from the immune-mediated event. The decision to re–challenge patients with atezolizumab should be based on investigator's assessment of benefit–risk and documented by the investigator (or an appropriate delegate).

6.1.2.13 *Immune-Mediated Myositis*

Immune-mediated myositis has been associated with the administration of atezolizumab. Myositis or inflammatory myopathies are a group of disorders sharing the common feature of inflammatory muscle injury; dermatomyositis and polymyositis are among the most common disorders. Initial diagnosis is based on clinical (muscle weakness, muscle pain, skin rash in dermatomyositis), biochemical (serum creatine kinase increase), and imaging (electromyography/MRI) features, and is confirmed with a muscle biopsy. Patients with possible myositis should be referred to a rheumatologist or neurologist. Patients with possible myositis should be monitored for signs of myocarditis.

Patients with signs and symptoms of myositis, in the absence of an identified alternate etiology, should be treated according to the guidelines in the table below

Event	Management
Immune-mediated myositis, Grade 1	
• Continue atezolizumab.• Refer patient to rheumatologist or neurologist.• Initiate treatment as per institutional guidelines.

Event	Management
Immune-mediated myositis, Grade 2	
Withhold atezolizumab for up to 12 weeks after event onset.^aRefer patient to rheumatologist or neurologist.Initiate treatment as per institutional guidelines.Consider treatment with corticosteroids equivalent to 1–2 mg/kg/day IV methylprednisolone and convert to 1–2 mg/kg/day oral prednisone or equivalent upon improvement.If corticosteroids are initiated and event does not improve within 48 hours after initiating corticosteroids, consider adding an immunosuppressive agent.If event resolves to Grade 1 or better, resume atezolizumab.^bIf event does not resolve to Grade 1 or better while withholding atezolizumab, permanently discontinue atezolizumab.^c
Immune-mediated myositis, Grade 3	
Withhold atezolizumab for up to 12 weeks after event onset.^aRefer patient to rheumatologist or neurologist.Initiate treatment as per institutional guidelines.Respiratory support may be required in more severe cases.Initiate treatment with corticosteroids equivalent to 1–2 mg/kg/day IV methylprednisolone, or higher-dose bolus if patient is severely compromised (e.g., cardiac or respiratory symptoms, dysphagia, or weakness that severely limits mobility); convert to 1–2 mg/kg/day oral prednisone or equivalent upon improvement.If event does not improve within 48 hours after initiating corticosteroids, consider adding an immunosuppressive agent.If event resolves to Grade 1 or better, resume atezolizumab.^bIf event does not resolve to Grade 1 or better while withholding atezolizumab, permanently discontinue atezolizumab.^cFor recurrent events, treat as a Grade 4 event.
Immune-mediated myositis, Grade 4	
Permanently discontinue atezolizumab.^cRefer patient to rheumatologist or neurologist.Initiate treatment as per institutional guidelines.Respiratory support may be required in more severe cases.Initiate treatment with corticosteroids equivalent to 1–2 mg/kg/day IV methylprednisolone, or higher-dose bolus if patient is severely compromised (e.g., cardiac or respiratory symptoms, dysphagia, or weakness that severely limits mobility); convert to 1–2 mg/kg/day oral prednisone or equivalent upon improvement.If event does not improve within 48 hours after initiating corticosteroids, consider adding an immunosuppressive agent.If event resolves to Grade 1 or better, taper corticosteroids over ≥ 1 month.

Event	Management
-------	------------

^a Atezolizumab may be withheld for a longer period of time (*i.e.*, >12 weeks after event onset) to allow for corticosteroids (if initiated) to be reduced to the equivalent of ≤ 10 mg/day oral prednisone. The acceptable length of the extended period of time must be based on an assessment of benefit–risk by the investigator and in alignment with the protocol requirements for the duration of treatment and documented by the investigator.

^b If corticosteroids have been initiated, they must be tapered over ≥ 1 month to the equivalent of ≤ 10 mg/day oral prednisone before atezolizumab can be resumed.

^c Resumption of atezolizumab may be considered in patients who are deriving benefit and have fully recovered from the immune-mediated event. The decision to re–challenge patients with atezolizumab should be based on investigator's assessment of benefit–risk and documented by the investigator (or an appropriate delegate).

6.1.2.14 *Hemophagocytic Lymphohistiocytosis and Macrophage Activation Syndrome*

Immune-mediated reactions may involve any organ system and may lead to hemophagocytic lymphohistiocytosis (HLH) and macrophage activation syndrome (MAS), which are considered to be potential risks for atezolizumab.

Patients with suspected HLH should be diagnosed according to published criteria by McClain and Eckstein (2014). A patient should be classified as having HLH if five of the following eight criteria are met:

- Fever $\geq 38.5^{\circ}\text{C}$
- Splenomegaly
- Peripheral blood cytopenia consisting of at least two of the following:
 - Hemoglobin <90 g/L (9 g/dL) (<100 g/L [10 g/dL] for infants <4 weeks old)
 - Platelet count $<100 \times 10^9/\text{L}$ (100,000/mcL)
 - ANC $<1.0 \times 10^9/\text{L}$ (1000/mcL)
- Fasting triglycerides >2.992 mmol/L (265 mg/dL) and/or fibrinogen <1.5 g/L (150 mg/dL)
- Hemophagocytosis in bone marrow, spleen, lymph node, or liver
- Low or absent natural killer cell activity
- Ferritin >500 mg/L (500 ng/mL)
- Soluble interleukin 2 (IL-2) receptor (soluble CD25) elevated ≥ 2 standard deviations above age-adjusted laboratory-specific norms

Patients with suspected MAS should be diagnosed according to published criteria for systemic juvenile idiopathic arthritis by Ravelli *et al.* (2016). A febrile patient should be classified as having MAS if the following criteria are met:

- Ferritin >684 mg/L (684 ng/mL)
- At least two of the following:
 - Platelet count $\leq 181 \times 10^9/\text{L}$ (181,000/mcL)
 - AST ≥ 48 U/L

- Triglycerides $>1.761 \text{ mmol/L (156 mg/dL)}$
- Fibrinogen $\leq 3.6 \text{ g/L (360 mg/dL)}$

Patients with suspected HLH or MAS should be treated according to the guidelines in the table below.

Event	Management
Suspected HLH or MAS	
• Permanently discontinue atezolizumab.• Consider patient referral to hematologist.• Initiate supportive care, including intensive care monitoring if indicated per institutional guidelines.• Consider initiation of IV corticosteroids, an immunosuppressive agent, and/or anti-cytokine therapy.• If event does not respond to treatment within 24 hours, initiate treatment as appropriate according to published guidelines (La Rosée 2015; Schram and Berliner 2015; La Rosée et al., 2019).• If event resolves to Grade 1 or better, taper corticosteroids over $\geq 1 \text{ month}$.

HLH = hemophagocytic lymphohistiocytosis; MAS = macrophage activation syndrome.

6.2 Recombinant Human IL-7 (CYT107)

There will be no dose reduction for CYT107 in this study.

Delays in dosing will be allowed for delays such as weather factors resulting in delays getting to the clinic or hospital, travel delays, clinic schedules, or emergencies. A delay of up to *72 hours* will be allowed on one occasion during the course of a treatment cycle.

Patients will come off protocol therapy if any CYT107 or treatment-related grade 3 or 4 AEs by CTCAE Version 5.0 criteria occur with the *exception* of transient lymphopenia. Three cases of Grade 3 lymphopenia have been documented with CYT107. Peripheral lymphopenia after the first CYT107 injection is a sign of CYT107 activity; reflecting the *rhIL-7* ‘homing effect’ of lymphocytes to deep tissues.

For purposes of this trial, since peripheral lymphopenia is a transient event, a Grade 3 ‘lymphocyte count decrease’ to $<500\text{-}200 \text{ cells/mm}^3$ and a Grade 4 ‘lymphocyte count decrease’ to $<200 \text{ cells/mm}^3$ will not require patients coming off protocol provided the lymphocyte count returns to a minimum of 500 cells/mm^3 by the time of the scheduled start of the next weekly dose within the treatment phase. A Grade 3 or 4 ‘lymphocyte count decrease’ will require patients coming off protocol if the count fails to return to a minimum of 500 cells/mm^3 by the time of the scheduled start of the next weekly dose.

Dose modifications for Adverse Events: Substantial AEs are not expected and thus dose modifications are not planned or recommended. In all human trials with CYT107, AEs were frequent, but transient and grade 2 or less (as noted in the Adverse Event list, [Section 7.1.2](#)). These include injection site reactions, lymphadenopathy, pyrexia, rash, and fatigue.

Below are dose management tables for the following AEs: fatigue, nausea, vomiting, diarrhea, neutropenia, thrombocytopenia, and hepatic damage.

Event Name	Fatigue
Grade of Event	Management/Next Dose of CYT107
≤Grade 1	No change in dosing schedule
Grade 2	No change in dosing schedule
Grade 3	Hold* until ≤Grade 2
Grade 4	Off protocol therapy
*Patients requiring a delay of >72 hours should go off protocol therapy.	
Recommended management: Physician discretion	

Event Name	Nausea
Grade of Event	Management/Next Dose of CYT107
≤Grade 1	No change in dosing schedule
Grade 2	No change in dosing schedule
Grade 3	Off protocol therapy if with adequate/maximal medical intervention symptoms persist
Grade 4	Off protocol therapy
Patients requiring a delay of >72 hours should go off protocol therapy.	
Recommended management: Antiemetics	

Event Name	Vomiting
Grade of Event	Management/Next Dose of CYT107
≤Grade 1	No change in dosing schedule
Grade 2	No change in dosing schedule
Grade 3	Off protocol therapy if with adequate/maximal medical intervention symptoms persist
Grade 4	Off protocol therapy
Patients requiring a delay of >72 hours should go off protocol therapy.	
Recommended management: Antiemetics	

Event Name	Diarrhea
Grade of Event	Management/Next Dose of CYT107
≤Grade 1	No change in dosing schedule
Grade 2	No change in dosing schedule
Grade 3	Off protocol therapy if with adequate/maximal medical intervention symptoms persist
Grade 4	Off protocol therapy
Patients requiring a delay of >72 hours should go off protocol therapy.	
Recommended management: Physician discretion	

Event Name	Neutropenia
Grade of Event	Management/Next Dose of CYT107
≤Grade 1	No change in dosing schedule
Grade 2	No change in dosing schedule
Grade 3	Hold* until ≤Grade 2
Grade 4	Off protocol therapy

*Patients requiring a delay of >72 hours should go off protocol therapy.

Recommended management: Treatment of infection as appropriate

Event Name	Thrombocytopenia
Grade of Event	Management/Next Dose of CYT107
≤Grade 1	No change in dosing schedule
Grade 2	No change in dosing schedule
Grade 3	Off protocol therapy
Grade 4	Off protocol therapy

Patients requiring a delay of >72 hours should go off protocol therapy.

Recommended management: Platelet transfusions if indicated

Event Name	Hepatic Damage
Grade of Event	Management/Next Dose of CYT107
≤Grade 1	No change in dosing schedule
Grade 2	No change in dosing schedule ¹
Grade 3	Off protocol therapy
Grade 4	Off protocol therapy

Patients requiring a delay of >72 hours should go off protocol therapy.

Recommended management: Physician discretion

Note: ¹CYT107 will be discontinued if patients have a concurrent elevation of ALT >3 × ULN and total bilirubin >2 × ULN in whom there is no evidence of biliary obstruction or other causes that can reasonably explain the concurrent elevation.

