Regimens of weekly IL-7 at the 10 μ g/kg level demonstrate an acceptable safety profile with very few grade 3 or 4 adverse events. More than 380 patients have been exposed to CYT107, including 236 patients in 7 phase I/IIa dose escalation studies with CYT107 in oncology, hematopoietic stem cell transplantation (HSCT), human immunodeficiency virus (HIV), hepatitis C virus (HCV) and hepatitis B virus (HBV) infected patients and 2 phase II studies in patients with HIV. CYT107 has been well tolerated [CYT107 Investigator's Brochure]. The most frequent adverse events are:

injection site reactions, lymphadenopathy, pyrexia, rash, and fatigue. A cumulative 819 administrations of CYT107 triggered 555 injection site reactions AE, *i.e.*, 70% of CYT107 administrations led to at least one injection site reaction. The worst grade reported was grade 2 in 159 of 819 administrations (19.4%). No grade 3 or 4 injection site reactions were reported.

Among the 555 injection site reactions related to CYT107:

- 113 (20.3%) were of grade <1
- 283 (51.0%) were of grade 1
- 159 (28.7%) were of grade 2
- No grade 3 or 4 injection site reactions were reported.

Of note, this scoring was performed with reference to the DAIDS 2.0 scale which is more severe than CTCAE scoring.

One true anaphylactic reaction and 4 acute allergic reactions have been reported, strictly in studies with repeated cycles of CYT107. The immunogenicity frequency and the occurrence of NADA (neutralizing antibodies) are higher with the exposure to multiple cycles of CYT107.

Two studies analyzed the pharmacokinetics of CYT107 in patients with HIV-1 with CD4 T-cell counts of 101-400 cells/ μ L and plasma HIV RNA <50 copies/mL while receiving highly active antiretroviral therapy (HAART) for \geq 12 months. Three dose levels of CYT107 were tested sequentially: 10, 20 and 30 μ g/kg. Increasing doses induced a dose response increase in peripheral blood T cells. The increases were nonlinearity above 20 μ g/kg/week in the lymphopenic patients and above 30 μ g/kg/week for the non-lymphopenic patients. The nonlinearity was presumed to be to the administered IL-7 being cleared by binding to an increased number of T cells, *i.e.*, a "Target Mediated Drug Disposition" [CYT107 Investigator's Brochure].

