4.5 General Guidelines

After registration, patients should begin protocol treatment within 5 business days. Issues that would cause treatment delays should be discussed with the PI. If a patient does not receive protocol therapy after registration, the patient's registration on the study may be canceled. The Clinical Research Site (CRS) must notify the CITN Coordinating Center of cancellations as soon as possible.

Except in very unusual circumstances, each participating institution will order DCTD-supplied agents directly from CTEP.

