5.1.2 Recombinant Human IL-7 (CYT107)

Patients enrolled in the Safety Run-in phase and patients randomly assigned to the experimental arm of the trial will receive recombinant human IL-7 (CYT107). The patients will receive 10 mcg/kg of IL-7 (CYT107) IM on days 1, 8, 15 and 22 of Cycle 1 only. The CYT107 dose must be administered before atezolizumab on Day 8 of Cycle 1.

For patient with a Body Mass Index (BMI) >30, an adjusted body weight will be used to calculate the final dose the patient will receive. Please refer to [Appendix D](#) for details on the adjusted body weight calculation.

Patients receiving CYT107 will have their vital signs (heart rate, respiratory rate, blood pressure, and temperature) determined within 60 minutes before the first CYT107 injection on day 1, and 2 hours (\pm 15 minutes) after the injection.

On day 8, vital signs will be monitored as described above ([Section 5.1.1](#)) following the guidelines for the first atezolizumab infusion.

On days 15 and 22, vital signs will be determined within 60 minutes before and within 30 minutes after the injection.

Patients will be informed about the possibility of the development of an allergic reaction to CYT107 (hives, bronchospasm, rash, etc.) and instructed to contact their study physician if they develop such symptoms.

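### Section 6.2 gives two incompatible stopping instructions for related grade 3 events: five of the seven grade 3 table rows conflict with the general rule, and the stopping term is not defined

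*Combined protocol and SAP*

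**What the plan says.** Section 6.2 opens its toxicity guidance with a general rule: "Patients will come off protocol therapy if any CYT107 or treatment-related grade 3 or 4 AEs by CTCAE Version 5.0 criteria occur". The one stated exception is transient lymphopenia, and its limit is spelled out: a grade 3 or 4 fall in lymphocytes "will require patients coming off protocol if the count fails to return to a minimum" by the next scheduled weekly dose.

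Seven event tables follow, each headed by a column on management and the next CYT107 dose. For grade 3 fatigue and grade 3 neutropenia the instruction is "Hold* until ≤Grade 2". For grade 3 nausea, vomiting and diarrhea it is "Off protocol therapy if with adequate/maximal medical intervention symptoms persist". Grade 3 thrombocytopenia, grade 3 hepatic damage and every grade 4 row are an unconditional stop. The tables carry a footer: "Patients requiring a delay of >72 hours should go off protocol therapy".

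Section 5.1.2 gives CYT107 "on days 1, 8, 15 and 22 of Cycle 1 only". Section 6.1 has separate tables for atezolizumab, many of which withhold the drug at grade 3 and resume it on recovery.

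**The concern.** A related grade 3 event in any of five categories falls under two instructions in the same section. If it recovers or responds in time, one instruction ends protocol therapy and the other allows the next CYT107 dose. A site cannot follow both. Two sites could treat the same patient differently, and either course could be recorded as a deviation.

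This is foremost a safety-instruction problem in a new combination. The protocol foresees such events: it provides tables for them, and Section 5.2.2 exempts short-lived grade 3 nausea, vomiting, diarrhea and fatigue from the dose-limiting toxicity definition.

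The second difficulty is scope. If *off protocol therapy* means CYT107 only, the consequence is at most three lost injections. If it means both agents, the patient also loses atezolizumab, and the rule collides with Section 6.1.

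**Working it through.** There is no plan figure to reproduce. The check is a row-by-row comparison of the general rule with the tables in Section 6.2, followed by a reading of the stopping term against the rest of the protocol.

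**Step 1. Grade 3 rows against the general rule (stop for any related grade 3 or 4 event).**

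| Event | Grade 3 instruction in the table | Agrees with general rule? |
|---|---|---|
| Fatigue | Hold; off only if the delay exceeds 72 hours | No |
| Nausea | Off only if symptoms persist | No |
| Vomiting | Off only if symptoms persist | No |
| Diarrhea | Off only if symptoms persist | No |
| Neutropenia | Hold; off only if the delay exceeds 72 hours | No |
| Thrombocytopenia | Off | Yes |
| Hepatic damage | Off | Yes |

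In conflict: 2 holds + 3 conditional stops = 5 of 7. In agreement: 2 of 7. All 7 grade 4 rows are off, so 2 + 7 = 9 of the 14 grade 3 and 4 rows agree. The conflict is confined to grade 3.

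**Step 2. When the two instructions give different results.** Three conditions must hold together.
- The event is related. The general rule covers only related events; the tables state no attribution limit.
- It recovers with a delay of no more than 72 hours, or responds to treatment. Otherwise both texts stop.
- A CYT107 dose is still due. Doses fall on Days 1, 8, 15 and 22, so a next dose exists only after doses 1, 2 and 3. The conflict can affect doses 2 to 4, or 3 of 4 injections.

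Example: related grade 3 fatigue begins on Day 5 and is grade 2 by Day 8. The table allows the Day 8 injection; the general rule has already ended protocol therapy.

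**Step 3. What the patient comes off.** No text in the protocol defines *off protocol therapy* for Section 6.2.
- For CYT107 only: the section title and the table column heading both refer to CYT107.
- Against settling it there: Section 4.5 uses the same term for every registered patient ("If a patient does not receive protocol therapy after registration"). Control patients receive only atezolizumab, so the term cannot mean CYT107 alone in that place. Section 5.4 separates stopping protocol therapy from leaving the study without naming the agents. The lymphopenia paragraph speaks of coming off protocol, which is different again.

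**Step 4. Consequence if atezolizumab is included.** The general rule covers any related grade 3 or 4 event, not only the seven tabled ones. It then conflicts with these grade 3 withhold-and-resume entries for atezolizumab:
- diarrhea or colitis (6.1.2.3)
- hyperglycemia, symptomatic adrenal insufficiency and hypophysitis (6.1.2.4)
- amylase or lipase elevation, and pancreatitis (6.1.2.8)
- dermatologic events (6.1.2.9)
- myositis (6.1.2.13)

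Hepatic events (6.1.2.2) belong here too. The grade 3 or 4 entry discontinues atezolizumab, but its footnote c lets resumption be considered after full recovery in a patient deriving benefit. Section 6.2 has no such allowance. On this reading the limits in Step 2 on Cycle 1 and doses 2 to 4 no longer apply, because atezolizumab may continue for up to 2 years.

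**The case against.** The strongest defence is that specific text overrides general text, so a site would follow the table for a tabled event. That is a sensible way to read many protocols, but this one does not say it. The general rule does not mention the tables, and it already names its single exception with that exception's own recovery condition. A second defence is that the tables are for unrelated events, since they state no attribution. That is not written either, and a related event meets the terms of both texts.

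A third defence is that the situation is rare: Section 2.2.2.3 reports, for weekly IL-7 at this dose level, "an acceptable safety profile with very few grade 3 or 4 adverse events". That stands as evidence on CYT107 alone. The general rule also covers treatment-related events, and Section 2.2.1.3.2 gives 13.7% (86 of 629) treatment-related grade 3 or 4 events with atezolizumab alone. Neither figure is for the combination, for these five events or for the CYT107 dosing period, so the documents do not settle the frequency.

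On scope, it is fair to say that the CYT107 title and column heading favour a CYT107-only meaning. A reader might infer that Section 6.2 definitely stops both agents and therefore contradicts Section 6.1. The documents do not support that; it holds only on the whole-regimen reading. A reader might also infer that atezolizumab exposure will differ between arms and bias the response comparison. That rests on the same unproven reading and on an event rate the documents do not give.

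**Conclusion.** The contradiction is real and lies on the face of Section 6.2: 5 of 7 grade 3 rows conflict with the general rule, while the other 2 and all 7 grade 4 rows agree. It applies to related events that recover or respond while CYT107 dose 2, 3 or 4 is still due. That rests on the wording alone, with no numerical assumption.

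That the stopping term is undefined is also established. The further conflict with Section 6.1 is conditional: it exists only if *off protocol therapy* includes atezolizumab, and in that case it is wider than the tabled events and not limited to Cycle 1.

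The number of patients affected cannot be computed, and no effect on objective response rate or progression-free survival can be stated. The point should be fixed because the instruction bears on patient safety and cannot be followed as written, not because it threatens the primary analysis.

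**What to change.** Reconcile the general rule in Section 6.2 with the grade 3 rows for fatigue, neutropenia, nausea, vomiting and diarrhea, and say which text governs when both apply. Define *off protocol therapy* once, state whether it covers CYT107 only or atezolizumab as well, use one wording throughout Section 6.2, and check the result against the atezolizumab tables in Section 6.1, including footnote c for hepatic events. Which rule stands is a decision for the sponsor's clinicians.

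The cost is a wording amendment, with no change to sample size or analysis.
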